5.3. Study intervention

A board-certified music therapist will facilitate the five sessions constituting the treatment sequence as follows:

- verbal processing of a) subjects' individual experiences and perceptions of stigma, and how those experiences have impacted their relationships, available resources, mental health, and treatment; and b) the specific misconceptions and inaccuracies that contributed to those experiences; culminating in a collaboratively composed song title;
- 2) reflection upon themes, metaphors, images, and symbols drawn from the discussion will inform collaborative lyric-writing. Additionally, the group will begin to make musical decisions based on discussion of preferred and relevant musical styles and genres, including the selection of one or more reference tracks. A reference track is an existing song that can be used as a stylistic or structural model.
- 3) group composition and arrangement;
- 4) rehearsing and recording the song; and
- 5) editing (mixing and mastering) and review.

The standard of care for ACU patients at HMH Carrier Clinic includes psychoeducational and verbal processing groups, and music therapy groups. MTAR exceeds the standard of care by offering a targeted treatment sequence that includes music therapy recording and self-advocacy.

5.4. Assignment / randomization

This prospective clinical trial's pseudo cluster randomized controlled design will take advantage of the unit's two separate residential areas ("wings") to control for contamination bias by randomizing treatment and control conditions to each wing, rather than each individual subject (see Figure 1 above).

5.5. Section of instruments (to include for all studies with a social behavioral intervention)

Internalized stigma will be assessed after enrollment, within 3 days of admission to the hospital (pretest/baseline), at ten days (posttest), and at 3 weeks after baseline (follow-up), using the Internalized Stigma of Mental Illness Inventory (Ritsher et al., 2003; Appendix 2). The ISMI is a widely-used measure with acceptable internal consistency (α = .72-.90) and test–retest reliability (r = .68-.92; Boyd et al., 2014; Chang et al., 2016). It was selected over the Perceived Devaluation and Discrimination Scale (PDD; Link, 2987) and Self-Stigma in Mental Illness Scale (SSMOI; Tucker et al., 2013) due to concerns about internal consistency and psychometric properties of these measures (Brohan et al., 2010).

5.6. Data collection (data points, source and storage)

Data points will include the subject's name, diagnoses, and treatment ID number, to be collected from the medical chart by research staff; and ISMI score, collected from the subject by questionnaire administered by the PI. Data will be collected by research staff and entered into REDCap, a secure web application.

The participant's file as it relates to this study will only be altered by the PI, who is also the clinician implementing the intervention. After each session (and only at this time), the PI will briefly document the group topic and the patient's affect and presentation as observed. For example: "(*Participant first name*) participated in a music therapy songwriting group focused on themes of stigma and resilience. (*Participant first name*) initially presented with a blunted, flat affect, becoming more activated and brightening by the end of the session. (*He/she/they*) participated by verbally suggesting the genre '(*genre*)' and song title '(*song title*)' for the project." Documentation related to the study will not be differentiated in the participant's file from other therapeutic group activity.

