After enrollment and consent, research staff will administer the ISMI in hard copy to establish a pretest baseline. After the treatment sequence of 5 group music therapy sessions, research staff will administer the ISMI in hard copy for post-test data. The ISMI will be administered by phone or in person by research staff for 3-week follow-up data.

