5.2. Recruitment, enrollment and retention (including screen failures as applicable)

The consent process will take place in a private room in the acute care unit and will be overseen by [name], MT-BC, the principal investigator. The process will take 15 to 20 minutes, during which time research staff will orient the participant to the study and go over the study protocols in detail as indicated in the consent form, making sure that participant understands its content. Potential participants will be provided with the opportunity to ask any questions or take the consent form to their room and make a decision later. The participant will sign the informed consent upon complete understanding of its content and agreement on participation in the study.

Subjects who are discharged or noncompliant during the treatment phase will be dropped from the study, and no further data will be collected from these subjects. Data that has been collected will remain.

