5.7. Follow-up and end-of study

Subjects will be hospitalized for at least the first two phases of data collection (pretest and posttest). The 3 week follow-up data may be collected either post-discharge or in the hospital, as required by the subject's unique treatment needs.

Subjects will be hospitalized for at least the first two phases of data collection (pretest and posttest), which will be administered in hard copy by research staff. The 3 week follow-up data may be collected by research staff either post-discharge by phone or in person in the hospital by hard copy, as required by the subject's unique treatment needs.

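### Section 5.6 has the therapist who delivers MTAR administer the self-reported primary outcome, while sections 4.3 and 5.7 give that task to research staff

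*Combined protocol and SAP*

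**What the plan says.** The protocol answers the question of who administers the ISMI in two ways.

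- **Section 5.6** divides data collection within one sentence. Name, diagnoses and ID number are "to be collected from the medical chart by research staff", whereas the ISMI score is "collected from the subject by questionnaire administered by the PI". The next paragraph says the participant's file "will only be altered by the PI, who is also the clinician implementing the intervention". Between these two statements, 5.6 also says more generally that research staff collect the data and enter them in REDCap.
- **Section 6.6** names the PI as the person who collects data.
- **Section 4.3** says "research staff will administer the ISMI in hard copy for post-test data", and makes the same assignment for the pretest. For the last time point: "The ISMI will be administered by phone or in person by research staff for 3-week follow-up data".
- **Section 5.7** repeats this for pretest and post-test, "which will be administered in hard copy by research staff", and has research staff collect the 3-week data "either post-discharge by phone or in person in the hospital by hard copy".
- **Section 5.2** has the PI oversee consent, "during which time research staff will orient the participant to the study".

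The protocol does not define research staff. Nothing in it requires the person who administers the ISMI to be independent of treatment delivery. Section 6.8 refers to treating clinicians in the plural, so the PI may not be the only session leader.

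**The concern.** The ISMI is the only outcome measure, and it is a self-report of agreement with statements about stigma. MTAR patients spend five sessions discussing and refuting stigma with the therapist. If that therapist then hands over the form, or reads the items by phone, treated patients may give the answers they think are hoped for. Controls have no MTAR sequence (Table 4) and so no matching reason to do so.

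Timing makes this hard to repair in the analysis. The pretest comes before the first session, so baseline scores carry no trace of the effect. It would appear only later and only in the MTAR arm, which is the pattern that a group-by-time comparison reads as benefit. That the shift would favour MTAR is a judgement; the documents do not establish it.

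**Working it through.** **Setting the sections side by side**

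| Task | 4.3 | 5.6 | 5.7 | 6.6 |
|---|---|---|---|---|
| ISMI pretest and post-test | research staff | PI | research staff | PI (data in general) |
| ISMI at 3 weeks | research staff | PI | research staff | PI (data in general) |
| Chart data | – | research staff | – | PI (data in general) |

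There are two ways to read this.

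1. *Research staff and PI are different people.* Section 5.6 supports this by giving the two data sources to different parties in one sentence, and 5.2 also mentions them separately. Then 5.6 contradicts 4.3 and 5.7.
2. *Research staff includes the PI.* Then the sections can be reconciled, but only because all of them allow the treating therapist to administer the primary outcome.

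Under either reading nothing prevents the exposure. Under the second, copying the 4.3 wording into 5.6 would not cure it, because the term itself has to be defined.

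**How strong the pathway is at each time point**

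- Pretest: no session has taken place, so no differential effect through MTAR is expected.
- Post-test (primary outcome): the form is on paper, and Appendix 2 asks respondents to mark their own answers. The pathway is the therapist's presence, not an interview.
- Three weeks: the ISMI may be given by phone, so answers may be spoken to the administrator. The risk is greatest here. This score is listed among the secondary (3.6) and exploratory (3.8) variables.

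**Illustration of size**

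The plan states no bias, so there is no figure of its own to reproduce.

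Inputs:
- 50 patients per arm (5.8.1) and alpha 0.05 (5.8.2).
- Two time points, pretest and post-test (3.4), with the treatment effect taken as the group-by-time term.
- Pre-post correlation r: not given. The values 0.68 and 0.92 are the ends of the test–retest range in 4.3 and 5.5; 0.3 and 0.5 are assumed, because correlation across a treated acute admission may be lower.
- Differential shift b = 0.1, 0.2 or 0.3 SD: assumed.
- No true effect, SD = 1 at both times, patients independent.

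With two time points, the interaction F equals the squared t on change scores, with 98 degrees of freedom.

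SE = sqrt(2(1 − r)) × sqrt(2/50)

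- r = 0.3: sqrt(1.4) × 0.2 = 0.237
- r = 0.5: sqrt(1.0) × 0.2 = 0.200
- r = 0.68: sqrt(0.64) × 0.2 = 0.160
- r = 0.92: sqrt(0.16) × 0.2 = 0.080

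The rejection rate comes from the noncentral t with noncentrality b/SE (for example 0.2/0.200 = 1.0 at r = 0.5):

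| r | b = 0.1 | b = 0.2 | b = 0.3 |
|---|---|---|---|
| 0.3 | 7.0% | 13.3% | 24.1% |
| 0.5 | 7.9% | 16.8% | 31.8% |
| 0.68 | 9.5% | 23.6% | 45.9% |
| 0.92 | 23.6% | 69.7% | 96.0% |

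A normal approximation agrees to within 0.8 percentage points, and simulation (40,000 trials per setting) to within 0.3.

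**The case against.** **The conflict may be only apparent.** If research staff includes the PI, then 4.3, 5.6, 5.7 and 6.6 fit together, and the general sentence in 5.6 on data collection blurs the two roles. This is a fair reading, but it does not remove the problem, since the therapist may then administer the ISMI under every section.

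**The arms may differ less than this suggests.** Controls may know the PI from consent. Standard care on the unit also includes music therapy and verbal processing groups (4.1, 4.3, 5.3), and the protocol does not say who leads them. This stands as a limit on the size of the effect. Contact centred on stigma would still differ between arms.

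**The table does not measure this problem.** This also stands. The shifts are assumed, and the same arithmetic would describe bias from patients knowing their treatment, which an independent administrator would not remove. The table is therefore not the gain from the fix. The r = 0.92 row uses the top of a reliability range and is probably too high for this setting. Independence ignores delivery in groups of 5 to 7 and allocation by wing. The finding does not depend on these figures.

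**Other staff may not exist.** The study personnel list names a PI, statistical support and protocol development support, but no assessor. The list may be incomplete, but the cost is conditional on this.

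**Section 6.8 is thin evidence of several session leaders.** It is a general statement on certification, and other sections describe a single therapist. Covering other leaders is a precaution that costs little.

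**Conclusion.** The point holds. Section 5.6, supported by 6.6, conflicts with 4.3 and 5.7 on the natural reading. On the alternative reading, the protocol simply permits the treating therapist to administer the self-reported primary outcome. If that happens, the exposure is confined to the MTAR arm after baseline, and the planned repeated-measures ANOVA cannot separate it from a treatment effect.

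Its size is unknown. Under the stated assumptions, even the smallest case considered (0.1 SD, r = 0.3) lifts the type I error from 5% to about 7%, and 0.2 SD at r between 0.3 and 0.68 lifts it to about 13% to 24%. Paper self-completion limits the risk for the primary outcome; phone follow-up is the most exposed. The change should be made, but the point does not by itself invalidate the design.

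**What to change.** Amend 5.6 and 6.6 to agree with 4.3 and 5.7, and define the role once. Suggested text:

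> For administration and collection of the ISMI, in both arms and at all time points, research staff excludes the PI and anyone who leads any MTAR session in the trial. Pretest and post-test forms are self-completed on paper without a session leader present. The 3-week follow-up, by phone or on paper, is administered by staff under the same restriction.

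The restriction applies to the role; the same individual need not see a patient at every visit.

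**Cost.** This is mainly wording if a suitable person is already in place, because 4.3 and 5.7 already assign the work. The load is up to 100 × 3 = 300 administrations: 200 paper forms at pretest and post-test, and up to 100 follow-ups. The sponsor should confirm that someone other than the PI is available. Section 6.9 shows a grant of $4,943.77 and support for capital improvements; it does not itemise the grant and mentions no assessor cost. If nobody is available, the change needs added staff time. Scheduling becomes less flexible. Sample size and analysis do not change, and bias from patients knowing their own treatment remains.

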5.7. Follow-up and end-of study

Subjects will be hospitalized for at least the first two phases of data collection (pretest and posttest). The 3 week follow-up data may be collected either post-discharge or in the hospital, as required by the subject's unique treatment needs.

Subjects will be hospitalized for at least the first two phases of data collection (pretest and posttest), which will be administered in hard copy by research staff. The 3 week follow-up data may be collected by research staff either post-discharge by phone or in person in the hospital by hard copy, as required by the subject's unique treatment needs.

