4.1.1 Study Duration

The proposed study duration is one year, with eight months allotted for data collection, and four months allotted for data analysis. Subjects will be involved for a period of 21 days, including follow-up data collection (See Table 4). Results of this study can help inform the feasibility of collecting follow-up data from this population, as patient adherence to aftercare plans can be unpredictable.

Day	Treatment Group	Control Group

1-3	Enrollment, Pre- Test/Baseline	Enrollment, Pre-Test
4-10	Treatment Sequence	No Treatment Sequence
8-10	Post-Test	Post-Test
21	Follow-up data collected	Follow-up data collected

Table 4. Study Timeline Per Cohort

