4.3. Study procedures

Patients will be identified and referred upon admission to the Acute Care Unit at HMH Carrier Clinic by the treatment team (attending doctors, nurses, and social workers). All subjects who are anticipated to remain admitted to the unit for at least 7 days will be considered regardless of gender or racial/ethnic background with the exception of those less than 18 years of age.

Internalized stigma will be assessed within 3 days of admission (pretest/baseline), at ten days (posttest), and at 3 weeks from baseline (follow-up), using the Internalized Stigma of Mental Illness Inventory (Ritsher et al., 2003; Appendix 2). The ISMI is a widely-used measure with acceptable internal consistency (α = .72-.90) and test–retest reliability (r = .68-.92; Boyd et al., 2014; Chang et al., 2016). It was selected over the Perceived Devaluation

and Discrimination Scale (PDD; Link, 2987) and Self-Stigma in Mental Illness Scale (SSMOI; Tucker et al., 2013) due to concerns about internal consistency and psychometric properties of these measures (Brohan et al., 2010). Data collection will include the subject's name, diagnoses, treatment ID number, and ISMI score. Treatment effect will be measured by using a two-factor, mixed-design analysis of variance (ANOVA). A P value of less than 0.05 will be considered to indicate statistical significance.

Description of Procedures

The music therapy treatment group will utilize a certified music therapist to facilitate a series of 5 group music therapy sessions over the course of 5 to 7 consecutive weekdays. Groups will be composed of 5 to 7 patients and the MT. There is no standard number of sessions for interventions addressing internalized stigma, and the available literature varies from one session in a single day to twenty sessions over a period of months. Since the average length of stay for acute care unit patients is 7 to 10 days, 5 sessions is the maximum feasible number of sessions to complete the treatment sequence for shorter stays. Though patients typically receive daily music therapy groups as part of the standard of care, this study improves upon the standard of care by providing a protocolized intervention sequence targeted at reducing internalized stigma of mental illness.

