5.8.2. Statistical Analysis Plan

Primary Analysis

Treatment effect on the primary dependent variable (ISMI score) will be measured by using a two-factor repeated-measures analysis of variance (ANOVA). A P value of less than 0.05 will be considered to indicate statistical significance.

Secondary Analysis

Treatment effect on the secondary dependent variables (diagnosis category) will be measured by using a two-factor repeated-measures analysis of variance (ANOVA). A P value of less than 0.05 will be considered to indicate statistical significance.

Exploratory Analysis

Treatment effect on the exploratory variable (ISMI score 3 weeks after baseline) will be measured by using a two-factor repeated-measures analysis of variance (ANOVA). A P value of less than 0.05 will be considered to indicate statistical significance.

6 - Trial Administration

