Appendix 1: Data collected

PHI: Name; DSM-5 category of diagnosis: schizophrenia spectrum and other psychotic disorders, bipolar and related disorders, depressive disorders, anxiety disorders, no diagnosis

Non-PHI: Participant ID (#); ISMI Score pre-intervention/baseline (#); ISMI Score post-intervention (#); ISMI Score 3 week follow-up (#)

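### Three-week ISMI is taken by phone or on paper according to discharge, after paper at pre- and post-test, and mode is not recorded: within-arm change should not be read as persistence

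*Combined protocol and SAP*

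**What the plan says.** Section 5.7 places pre-test and post-test in hospital, "which will be administered in hard copy by research staff". The three-week assessment is collected "either post-discharge by phone or in person in the hospital by hard copy", the choice being made "as required by the subject's unique treatment needs". Section 4.3 agrees: "The ISMI will be administered by phone or in person by research staff for 3-week follow-up data".

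On timing, section 4.1.1 states: "Subjects will be involved for a period of 21 days, including follow-up data collection". Table 4 puts follow-up at Day 21. Section 4.3 reports that "the average length of stay for acute care unit patients is 7 to 10 days".

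Appendix 1 lists "ISMI Score 3 week follow-up" as a score only, with no field for mode, discharge status or date of assessment. Section 5.8.2 analyses the three-week score with a two-factor repeated-measures ANOVA at P<0.05. It has no mode term and no sensitivity analysis by mode, and it does not say which term of the ANOVA answers the persistence question. Sections 4.3 and 5.5 give reliability figures for the ISMI but cite no evidence that phone and paper scores are equivalent.

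The Introduction and section 3.2 define the effect as change from baseline compared with control. Section 3.7 makes persistence of that effect an exploratory objective, although section 3.6 also lists the three-week score among the secondary outcome variables.

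**The concern.** The change of mode nearly coincides with the follow-up visit. A subject who answers differently by phone than on paper will show a change at Day 21 that has nothing to do with stigma. Those who stay on paper are the patients still in hospital at three weeks, so mode is also tied to length of stay and clinical state.

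Two readings of the three-week data are exposed, to different degrees. Change within the MTAR arm from post-test to follow-up absorbs the whole mode effect among those phoned. The comparison between arms absorbs it only where the arms differ, either in the share phoned or in how phoning affects the answers. Neither balance is guaranteed, because discharge follows allocation. Without a mode field, nobody could check afterwards.

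**Working it through.** The plan gives no figure for mode, so there is none to reproduce. The question is how far a mode shift would carry into each contrast.

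**Inputs from the protocol.** Paper at pre- and post-test; phone if discharged and paper if in hospital at three weeks (4.3, 5.7). Average stay 7 to 10 days (4.3) against Day 21 (Table 4). Fifty per arm and f = 0.33 (5.8.1). For two groups d = 2f = 2 × 0.33 = 0.66, used here only as a yardstick.

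**Assumptions, not in the documents.** An additive mode shift m of 0.1 to 0.3 SD, sign unknown. A phoned share p of 90%. Analysed subjects must stay until post-test, so their stays may exceed the unit average and 90% is a guess. A difference in phoned share of 10 to 20 points between arms.

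**Formulas.**
- Bias in one arm's change to follow-up = p × m.
- Bias in the between-arm contrast = p(MTAR) × m(MTAR) − p(control) × m(control). With a common shift this is m × [p(MTAR) − p(control)].

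**Results, in SD.**

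| Shift m | Within arm, 90% phoned | Between arms, 10-point gap | Between arms, 20-point gap | 20-point gap as share of 0.66 |
|---|---|---|---|---|
| 0.1 | 0.09 | 0.01 | 0.02 | 3% |
| 0.2 | 0.18 | 0.02 | 0.04 | 6% |
| 0.3 | 0.27 | 0.03 | 0.06 | 9% |

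With equal phoned shares and a common shift, the between-arm bias is 0 whatever the size of m.

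**Effect on the tests.** Take 50 independent subjects per arm, no true effect, and an assumed correlation of 0.7 between assessments. (The test–retest range in 4.3 is .68 to .92.) The SD of change is √(2 × (1 − 0.7)) = 0.775. The standard error of the between-arm difference in change is 0.775 × √(2/50) = 0.155 SD. A bias of 0.06 SD is therefore 0.06/0.155 = 0.39 standard errors.

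Simulation with 20,000 replicates gave:
- 90% phoned in both arms, shifts of 0.1, 0.2 and 0.3 SD: the overall time effect was falsely significant in about 20%, 62% and 93% of trials. The group-by-time test rejected in 4.7%, 4.9% and 5.0%.
- 90% versus 70% phoned: the group-by-time test rejected in 5.8% at 0.2 SD and 6.6% at 0.3 SD. The same simulation gave 5.4% with no shift.
- 90% versus 50% phoned, 0.3 SD: bias 0.3 × 0.4 = 0.12 SD, rejection 11.7%. Nothing in the documents suggests so wide a gap.

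These runs ignore clustering by wing and by therapy group.

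**With one common mode.** Setting p = 1 in both arms makes the between-arm bias m × (1 − 1) = 0 for a common shift. Within-arm bias becomes m itself, 0.1 to 0.3 SD, slightly larger than before.

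**The case against.** The strongest reply is that the protocol never defines persistence as within-arm change. The Introduction and sections 3.2, 3.7 and 5.8.2 all speak of a treatment effect, which is relative to control, and no separate test within the MTAR arm is planned. The high false-positive rates above belong to the time effect, not to that contrast. This stands, and it limits the point. What remains is that section 5.8.2 does not name the term to be used, so a reader of the results could still take flat or falling MTAR scores as persistence.

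The second reply is that, if nearly everyone is discharged by Day 21, the phoned share is close to its ceiling in both arms and a 10 to 20 point gap is unlikely. This is fair: no passage points to such a gap, and the figures above show what one would do rather than predict it.

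Third, offering phone or bedside collection is a sensible way to keep follow-up complete in a population whose aftercare adherence section 4.1.1 calls unpredictable. That also stands, and the remedy should keep both routes.

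A reader might infer that spoken answers to staff are milder, so that the bias favours MTAR. The documents support neither that direction nor any size. Even self-completion on paper and reading aloud by phone are inferences: reasonable ones, since Appendix 2 asks respondents to mark answers, but section 5.7 does not spell them out.

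**Conclusion.** The point holds as a minor one. Mode at three weeks depends on discharge, differs for most subjects from the mode used earlier, and is neither recorded nor modelled. Within-arm change from post-test to follow-up therefore cannot be read as persistence. Under the assumed 0.1 to 0.3 SD shift and 90% phoned, it would be off by 0.09 to 0.27 SD.

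The planned between-arm contrast is biased only if the phoned share or the mode effect differs by arm. For a 10 to 20 point gap in phoned share the bias is 0.01 to 0.06 SD, at most about 9% of the planning effect. That range does not cover a mode effect that differs by arm. Such a difference is possible, because section 5.6 has the principal investigator, who also delivers the intervention, administer the questionnaire, while sections 4.3 and 5.7 say research staff.

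Two stronger readings are not supported. The three-week comparison with control is not shown to be invalid: with equal shares and a common shift its bias is zero. The primary pre/post comparison is not affected, since it is on paper throughout. Nor would recording mode alone repair the analysis, because mode follows discharge and a covariate could not separate the two.

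**What to change.** In sections 4.3 and 5.7, specify one scripted administration at Day 21 for every subject in both arms, for example staff reading the items aloud whether by phone or at the bedside. The script should name who administers it, the same role in both arms, which also settles the difference between section 5.6 and sections 4.3 and 5.7.

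Add mode, discharge status and date of assessment to Appendix 1 and REDCap. In section 5.8.2, state that persistence is concluded from the between-arm difference in change from baseline at Day 21, not from within-arm change. Day 21 follows Table 4. Sections 3.6 to 3.8 count three weeks from the end of treatment instead, and the two should be reconciled.

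The cost is a short script, three data fields and a few lines of text. Both collection routes are kept, so retention should not suffer. The downside is that the few subjects still in hospital also leave paper, so within-arm change to Day 21 stays confounded with mode. Phone and bedside may still differ somewhat, and the mode field cannot fully separate that from discharge status. Sending subjects home with a blank form to mark and read back is less attractive: some will lose it, which would probably recreate mixed modes.
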